Hereby, patients of the control arm shall receive serial cervical length measurements by transvaginal ultrasound (TVS) every 4 weeks started at 12+0 weeks.

A cerclage may be indicated when the cervical length is below 25 mm.¹ (s. consort-diagram).

Sample size:

For sample size calculation, we assume a combined event rate for the primary outcome (long-term survival without neurodevelopmental disability at 3 years of follow up) of 8% for the pessary group and an event rate of 20% for the control group van't Hooft 2016. Group sample size of 121 in both groups achieve 80% power to detect this difference using a two-sided chi-square test with significance level alpha=5%. To account for a drop out rate around 25%, sample size of 155 in each group, overall n=310 women will be recruited.

Study calendar:

Starting recruitment: June, 1st, 2018

Finishing recruitment and follow-up: est. June 1st, 2023.

Final report: Sept. 1st, 2023.

Table of contents

1. General Information

- 1.1. Title, protocol identifying number and date.
- 1.2. Name and address of the Sponsor.
- 1.3. Name and title of the authorized person by the Sponsor to sign the protocol and the protocol amendments.
- 1.4. Name, title, addresses and telephone numbers of the medical experts of the Sponsor of the trial.
- 1.5. Name and title of all the researchers who are responsible for conducting the trial and address and telephone numbers of trial sites.
- 1.6. Name, title, address and telephone number of the qualified physician who is responsible for all medical decisions on each trial site.
- 1.7. Name and address of the medical departments or institutions that are involved in the trial.

2. Rationale

- 2.1. Justification of the relevance of the trial.
- 2.2. Description of the study population.
- 2.3. Name and description of the device under investigation.
- 2.4. Statement that testing will be performed according to the protocol, GCP and applicable legal requirements.

3. Objective

4. Design

- 4.1. Specific description of primary and secondary variables.
 - 4.1.1. Primary outcome.
 - 4.1.2. Secondary outcomes.
- 4.2. Description of the trial design.

Confidential

- 4.3. Flowchart.
- 4.4. Description of the medical device and treatment regimen.
- 4.5. Expected duration of subject's participation.
- 4.6. Completion and interruption criteria of the study or the subjects.
- 4.7. Maintenance of the randomization codes and test procedures of the trial.

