2.2. Description of the study population.

Women with a singleton pregnancy at 12 – 16 weeks of gestation and a history of at least one previous preterm delivery before 34+0 weeks and/or a history of previous cervical surgery attending the reference hospital and who do not fulfil the exclusion criteria the study will be proposed. The patients will be informed of the intended therapeutic effect and possible side effects. If they agree and after obtaining their informed consent, they will be randomised according to either usual management with rescue cerclage placement only when (and as soon as possible) a cervical shortening below 25 mm occurs (=control group) or cervical pessary placement (= pessary group).

Pessaries or cerclage shall be placed up to 37+0 weeks of gestation. In the control group serial cervical length measurements shall be conducted every 4 weeks in order to diagnose cervical shortening as soon as possible.

2.3. Name and description of the device under investigation.

The Arabin cervical pessary, which is CE-certified for preventing SPB (CE 0482 / EN ISO 13485: 2012 + AC:2012 annex III of the council directive 93/42 EEC).

See annex I.

2.4. Statement that testing will be performed according to protocol, GCP and applicable legal requirements.

The Clinical Trial will be conducted following the protocol, the GCP, and all legal requirements.

3. Objective

This study aims to investigate the benefit of a prophylactic cervical pessary treatment in women at high risk of PTB due to a history of at least one previous preterm delivery before 34+0 weeks and/or a history of previous cervical surgery on the children's long-term survival without neurodevelopmental disability.

Hereby, a standardized and validated test called 'Ages and Stages 3rd edition'²⁷ should evaluate the children's neurodevelopment. The test should be conducted by the parents and takes approximately 12 minutes. The questionnaires will be provided by the sponsor.

4. Design

4.1. Specific description of primary and secondary variables.

4.1.1. Primary outcome:

- Children's long-term survival without neurodevelopmental disability

4.1.2. Secondary outcomes:

- Offspring
 - Time to birth
 - Preterm birth before 37 weeks: rate of delivery before 36+6 weeks
 - Preterm birth before 34 weeks: rate of delivery before 33+6 weeks

Confidential

[figure not shown]
[figure not shown]
- Preterm birth before 32 weeks: rate of delivery before 31+6 weeks

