 - Preterm birth before 30 weeks: rate of delivery before 29+6 weeks
 - Preterm birth before 28 weeks: rate of delivery before 27+6 weeks
 - Birth weight: median weight (g) of the newborns at birth
 - Fetal or neonatal death: rate of intrauterine demise or neonatal death during the first 24 hours
 - Neonatal morbidity: rate of major adverse neonatal outcomes before discharge from the hospital
 - Intraventricular Haemorrhage (IVH): grades III-IV
 - Retinopathy of prematurity
 - Respiratory Distress Syndrome (RDS): grades II-IV,
 - Need for ventilation > 72 h
 - Necrotising enterocolitis
 - Proven or suspected sepsis, antibiotics (>5 days)
 - Need (Duration in days) for neonatal special care (NICU)
 - Harm from intervention
- Mother:
- Maternal death
 - Significant maternal adverse events (rate):
 - Heavy bleeding: bleeding that requires a medical intervention
 - Cervical tear: cervical rupture due to the pessary placement
 - Uterine rupture: rupture of the uterus due to contractions or surgery
 - Physical or psychological intolerance to pessary: discomfort or pain due to the pessary that makes daily life uncomfortable (number of cases)
 - Rupture of membranes before 32 weeks: rate of—rupture of amniotic membranes before 31+6 weeks
 - Infection/inflammation
 - Hospitalisation for threatened preterm labour before 32 weeks: requirement of hospitalisation due to preterm contractions that need medical treatment to try to stop them before 31+6 weeks (rate)
 - Mean hospital stay duration: number of days of admittance at the hospital
 - Use of tocolytic treatment: Type of tocolytic, days of treatment, dose

4.2. Description of the trial design.

Open Multicentre International Collaborative Randomized Controlled Trial, in parallel groups, based on intention-to-treat analysis comparing the placement of a prophylactic cervical pessary with usual management in singleton pregnancies at high-risk of PTB due to a history of at least one previous preterm delivery before 34+0 weeks and/or a history of previous cervical surgery.

4.3. Flowchart.

Confidential

4.4. Description of the medical device and the treatment regimen.

The cervical pessary is a vaginal device (silicone ring) that is used to treat pregnant women for preventing spontaneous preterm birth. This device can be easily placed around the uterine cervix without pain (see annex I).

Confidential

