Women with a singleton pregnancy at 12+0 – 16+0 weeks of gestation and a history of at least one previous preterm delivery before 34+0 weeks and/or a history of previous cervical surgery attending the reference hospital for a preventive examination will be informed of the ongoing trial. The patient will be advised of the intended therapeutic effect and possible side effects. If they agree and after obtaining their informed consent, they will be randomised according to either usual management (=control group) or cervical pessary placement up to 37+0 weeks (=pessary group).

If the pregnant woman is assigned to the pessary group and after having excluded a vaginal infection the pessary will be inserted directly. This procedure does not need anaesthesia and it does not need to be done in a surgery room. After the insertion of the pessary the correct fit of the pessary is verified by transvaginal ultrasound and in case it does not fit perfectly, it can easily be adjusted.

In the control-group the cervical length of the women will be evaluated by transvaginal ultrasound scan started from randomization and every 4 weeks; if a cervical shortening below 25mm is detected a Mc Donald cerclage will be placed.

The pessary will be removed at 37+0 weeks of gestation, or before if any unexpected event occurs (see 4.6). After insertion of the pessary the obstetrical management during the remainder of the pregnancy will be usual management.

Further surveillance of the pregnancy will not be influenced by the participation on the study.

4.5. Expected duration of subject's participation.

Starting recruitment: June, 1st, 2018

Finishing recruitment and follow-up: est. June 1st, 2023.

Final report: Sept. 1st, 2023

4.6. Completion and interruption criteria of the study or the subjects.

The pessary will be removed at 37+0 weeks of pregnancy. The indications to remove them before this time will be: active bleeding stronger than period bleeding, persistent contractions after tocolysis and premature rupture of the membranes after 34+0 weeks.

After removing the pessary, the obstetrical management will be done as usual and will not be influenced by the study.

4.7. Maintenance of the randomisation codes and test procedures of the trial.

Every participating centre will have its own randomisation list.

We have created a database in a website so it can be accessed worldwide, that every hospital will be able to randomize their patients.

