The pessary will be inserted during a preventive examination in pregnancy in the examination room. This procedure does not need anaesthesia and it does not need to be done in a surgery room. After the insertion of the pessary the correct fit of the pessary is verified by transvaginal ultrasound and in case it does not fit perfectly, it can easily be adjusted. In the control-group the cervical length of the women will be evaluated by transvaginal ultrasound scan: if a cervical shortening below 25 mm is

Confidential

detected a cervical cerclage will be placed. The pessary or cerclage will be removed at 37+0 weeks of gestation, or before if any unexpected event occurs (see 4.6). After insertion of the pessary the obstetrical management during the pregnancy will be usual management. Further surveillance of the pregnancy will not be influenced by the participation on the study.

7. Efficacy assessment

7.1. Specification of efficacy parameters: Primary and secondary endpoints.

This study aims to investigate the benefit of a prophylactic cervical pessary treatment in women at high risk of PTB due to a history of at least one previous preterm delivery before 34+0 weeks and/or a history of previous cervical surgery on the perinatal outcome and on the children's long-term survival without neurodevelopmental disability.

The effect of the pessary treatment will be assessed in women independent of the cervical length at 12 -16 weeks of gestation compared to standard care treatment.

7.2. Methods and timing to assess records and analyze the efficacy parameters.

The pregnant women will be assessed according to usual obstetrical management in a high-risk pregnancy.

	Regular Preventive Exam	Serial CL measurements after randomization	Regular Preventive Exam 37 WoG	Postnatal evaluation	3 years follow up (corrected age)
Study procedure	study inclusion 12+0-16+0 WoG				
Informed consent	x				
randomisation	x				
Control-group		x			
Pessary/cerclage placement	Pessary-Group: Pessary at enrollment	Control-Group: Cerclage when CL \leq 25mm			
Pessary/cerclage removal	WoG 37+0		x		
physical exams					
Abdominal US	x	x	x		
Vaginal US		x			
pH-Value	pH < 4,4	pH < 4,4			
Neonatal examination				x	
Ages & Stages test					x
Exam at paediatrician					x

8. Assessment of Safety

8.1. Procedures to record and report adverse events.

Confidential

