To ensure no confusion or misunderstanding of the difference between the terms "serious" and "severe", which are not synonymous, the following note of clarification is provided:

The term "severe" is often used to describe the intensity (severity) of a specific event (as in mild, moderate, or severe myocardial infarction); the event itself, however, may be of relatively minor medical significance (such as severe headache). This is not the same as "serious," which is based on patient/event outcome or action criteria usually associated with events that pose a threat to a participant's life or functioning as defined in the bullet points above. Seriousness (not severity) serves as a guide for defining regulatory reporting obligations.

Serious Adverse Reaction (SAR): An adverse event (expected or unexpected) that is both serious and, in the opinion of the reporting investigator, believed with reasonable probability to be due to one of the study treatments, based on the information provided.

Suspected Unexpected Serious Adverse Reaction: A serious adverse reaction, the nature or severity of which is not consistent with the applicable product information

Confidential

(e.g. Investigator's Brochure for an unapproved investigational product or summary of product characteristics for an approved product).

8.3. Procedures for immediate notification of serious or unexpected adverse events.

All AEs occurring during the study /or observed by the investigator or reported by the participant, whether or not attributed to study medication, will be recorded on the CRF. The following information will be recorded: description, date of onset and end date, severity, and assessment of relatedness to study medication, other suspect drug or device and action taken. Follow-up information should be provided as necessary.

AEs considered related to the sanitary device, as judged by a medically qualified investigator, will be followed until resolution or the event is considered stable. All related AEs that result in a participant's withdrawal from the study or are present at the end of the study, should be followed up until a satisfactory resolution occurs.

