(2) The primary outcome will be evaluated 3 years after the last woman enrolled in this study has delivered her neonate.

Confidential

A descriptive analysis by preterm birth will be carried out calculating means and medians for quantitative variables and proportions with 95% confidence intervals for categorical variables.

Additionally we will perform an explorative subgroup analysis of the study collective comparing the efficacy of the cervical pessary treatment in women with a normal cervical length at 12 -16 weeks of gestation and in women who have developed a cervical shortening (< 25 mm) as an additional risk factor.

For the primary endpoint we expect to have a drop out rate of up to 25% due to the long follow-up time (3 years) of the study; but we do not expect to have lost data for the secondary endpoints because for these parameters the study has a short follow-up time till time to birth only.

An interim analysis shall be conducted on key safety parameters after birth of 150 neonates: the following safety endpoints will be assessed by a one-sided test with $\alpha=1\%$

- on level of the neonates:

rate of preterm birth, time to birth, birth weight, death, neonatal morbidity, harm of intervention

- and on the maternal level:

rate of hospitalisation for threatened preterm labour < 32 weeks, rate of P_{RoM} <32 weeks, rate of infection / inflammation, rate of physical or psychological intolerance to pessary, rate of SAR/SAE, death.

The trial will be terminated as negative if a disadvantage for the pessary-treatment can be found in one of these tests. To guarantee a high safety level the significance level is chosen more conservatively than in a Bonferroni correction. All analysis will be carried out with SPSS® version 19.0 or later (IBM Company SPSS Inc.

Headquarters, Chicago, Illinois, USA) and R version 3.2.3 or later (R Foundation for Statistical Computing, Vienna, Austria).

Primary Outcome	Statistical Test
Children`s Long-Term Survival without Neurodevelopmental Disability (3-Years-follow up)	Chi-Square test
Secondary Outcome	Statistical Test
Birth before 34 Weeks of Gestation	Chi-Square test or Fisher test
Time to Birth	Cox regression
Birthweight	t-test or Wilcoxon-Mann-Whitney test
Fetal / Neonatal Death	Chi-Square test or Fisher test
Neonatal Morbidity	Chi-Square test or Fisher test
Need for Hospitalization	Chi-Square test or Fisher test
Days of Hospitalization	t-test or Wilcoxon-Mann-Whitney test

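### Adverse events have no set enquiry or time points and only the control arm has named contacts before 37 weeks, so softer maternal events may be recorded unequally

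*Combined protocol and SAP*

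**What the plan says.** **Event capture.** Section 8.3 applies to "All AEs occurring during the study /or observed by the investigator or reported by the participant". It lists what to write down for each event but not how or when to ask. The 7.2 schedule has no adverse-event row.

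**Control arm.** Section 2.2: "In the control group serial cervical length measurements shall be conducted every 4 weeks". Section 4.4: "In the control-group the cervical length of the women will be evaluated by transvaginal ultrasound scan started from randomization and every 4 weeks". The synopsis likewise says that "patients of the control arm shall receive serial cervical length measurements by transvaginal ultrasound (TVS) every 4 weeks started at 12+0 weeks". None of these states the last scan week.

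**Pessary arm.** Section 4.4: "After insertion of the pessary the obstetrical management during the remainder of the pregnancy will be usual management". No study contact is named between insertion and removal at 37+0.

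**Both arms.** Section 7.2 says women are assessed under usual high-risk obstetric management. Sections 4.4 and 6.1 add: "Further surveillance of the pregnancy will not be influenced by the participation on the study". In the 7.2 table, the control-group mark falls in the serial-scan column, but the ultrasound and pH entries in that column carry no arm label.

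**Use of the data.** Section 9.1 compares maternal adverse events, vaginal infections and hospitalisation between arms. Its interim look, after 150 births, tests several maternal items one-sided at 1%, including infection/inflammation, SAR/SAE and "rate of hospitalisation for threatened preterm labour < 32 weeks". A pessary disadvantage on any one test stops the trial.

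**Notification.** Section 8.1 describes notifying the sponsor of serious unexpected effects for pessary treatment only, whereas 8.3 requires every SAE to be reported.

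**The concern.** A between-arm comparison of harms is only as good as the symmetry of the recording. Here the protocol gives control women a recurring study occasion at which an event can be observed or mentioned, and gives pessary women none of its own. The statement that surveillance is unaffected by participation does not fit with scans prescribed for one arm.

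The events at risk are those that someone must notice or ask about: infection or inflammation, bleeding, discomfort and non-serious adverse events. Pessary intolerance is a special case. It has no control-arm counterpart, so passive capture can only under-count it.

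If fewer of these events were captured on pessary, a real excess could be diluted in the final analysis and in the affected interim tests, or an apparent advantage could arise from recording alone. If the imbalance ran the other way, the pessary could look harmful without being so, and the interim rule would act on that.

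**Working it through.** **1. Named contacts after randomisation and before 37+0.** Inputs: entry at 12+0 to 16+0 and a 4-week interval (2.2, 4.4).
- Entry at 12+0: weeks 16, 20, 24, 28, 32, 36, so 6 scans.
- Entry at 16+0: weeks 20, 24, 28, 32, 36, so 5 scans.
- These counts assume scanning to 36 weeks. If scans stopped at 24 weeks they would be 3 and 2.
- Pessary arm: 0 named. Routine antenatal contacts come on top in both arms; the plan does not say how many.

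**2. Which outcomes are exposed.**
- Threatened-labour admission is defined in 4.1.2 as "requirement of hospitalisation due to preterm contractions that need medical treatment to try to stop them before 31+6 weeks", and tocolysis by type, days and dose. Both are care events found in hospital records.
- Hospitalisation makes an event serious (8.2), and all SAEs must be reported (8.3).
- Infection/inflammation, discomfort, bleeding short of admission and non-serious events depend more on being observed or asked about.

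**3. Illustration for the exposed events.** The plan states no figure for event capture that could be reproduced. As a check on the routine, its own case of 121 per arm, 8% versus 20%, two-sided 5%, gives 78% exact power, close to the stated 80%.

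Assumptions, none from the documents: the true rates, and a relative capture *d* on pessary, so that recorded pessary rate = *d* × true rate. Arm sizes are 155 at the final analysis (9.2) and about 75 at the interim (150 births, assumed split equally).

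With *a* and *b* events among *n* per arm and p̄ = (a + b)/(2n), the statistic is z = [(a − b)/n] / √[2p̄(1 − p̄)/n]. Power is the sum of the two binomial probabilities over all (a, b) with z above 1.96 (final, two-sided 5%, direction of interest) or above 2.326 (interim, one-sided 1%).

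| *d* | Recorded pessary rate (true 20%, control 10%) | Final power | Interim power | Equal true rates of 30%: P(significantly fewer on pessary), final |
|---|---|---|---|---|
| 1.00 | 20% | 70% | 26% | 2.5% |
| 0.95 | 19% | 62% | 21% | 5% |
| 0.90 | 18% | 53% | 17% | 8% |
| 0.80 | 16% | 35% | 10% | 22% |
| 0.70 | 14% | 19% | 5% | 44% |

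The interim column applies only to a softer interim endpoint such as infection/inflammation; the interim list has no general adverse-event rate.

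**4. Sensitivity to the assumed rates.** For a true 45% versus 30%, final power is 79% at *d* = 1, then 49%, 20% and 5% at 0.9, 0.8 and 0.7. In general the recorded relative risk is *d* × RR, so the excess vanishes at *d* = 1/RR: 0.5 for 20% versus 10%, and 0.67 for 45% versus 30%.

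**5. Opposite direction.** By symmetry, if the control arm were the one under-recorded, with equal true rates of 30%, a false finding of more events on pessary would have the same final probabilities: 5%, 8%, 22% and 44%. At the interim (n = 75, z > 2.326) the chance of a false harm signal on that endpoint would go from 1% to about 2%, 3%, 7% and 14%.

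**The case against.** Four arguments count against the point.

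- **Pessary women are seen.** They attend usual high-risk care, and the unlabelled ultrasound and pH entries in 7.2 may apply to them too. The exploratory subgroup in 9.1, defined by developed cervical shortening, may itself need cervical length in both arms. This stands: a reader might infer that pessary women go unobserved until 37 weeks, and the documents do not say so. What remains is that the plan names contacts for one arm only and leaves the rest unclear.
- **The heavier outcomes do not depend on visits.** A reader might infer that threatened-labour admissions and tocolysis are looked for unequally. They are defined by care given and come from hospital records. Scans may change how often they happen, but scanning with cerclage is the comparator strategy, so that is a difference in care and not a detection error. The maternal adverse-event row in 9.1 may also mean mainly the graver items listed in 4.1.2, which would shrink the exposed part.
- **The direction is not established.** A reader might infer that the error must favour the pessary. Pessary-only notification in 8.1, follow-up of device-related events to resolution in 8.3 and open-label reporting could each raise pessary counts. The net sign is unknown.
- **The capture rates are assumed.** Nothing in the documents supports 70%. At 95% to 100% capture, final power is 62% to 70% and the false-benefit rate 2.5% to 5%. Section 8.3 also begins with all events that occur, so it is not expressly limited to passive capture. It gives no means of finding them, however.

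None of these supplies the missing element, which is a common enquiry at common times.

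**Conclusion.** The concern holds for maternal events that must be noticed or asked about. Capture is unstructured, the trial is open-label, and the only protocol-named contacts between enrolment and 37 weeks belong to the control arm. Recording can therefore be unequal; it can favour the pessary, but the sign is not determined.

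The size is unknown. It is modest if relative capture is about 95% and large if it is 80% or lower. The figures rest on assumed event rates, assumed capture and, for the interim, an equal split of 150 births. They should not be applied to admissions, tocolysis or SAEs involving hospitalisation. The documents do not support the wider conclusion that the harm comparison as a whole is unreliable. The primary outcome is not affected. This is a cheap improvement worth making, not a fatal flaw.

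**What to change.** - **7.2 and 8.3:** add one structured adverse-event form, completed at the same gestational ages in both arms, at routine antenatal contacts or from the maternity record. Add an adverse-event row to the schedule, label the ultrasound and pH entries by arm, and state the last scan week as already intended.
- **9.1:** base the interim and final comparisons of softer maternal events on this form.
- **Admissions and tocolysis:** take them from hospital records in both arms, with the trigger noted. State in 9.1 that a difference may partly reflect the control-arm scans.
- **8.1:** apply the notification wording to both arms, in line with the SAE reporting in 8.3.
- **4.4 and 6.1:** reconcile the statement on unchanged surveillance with the control-arm scans.
- **Analysis set:** keep all events in the intention-to-treat comparison. Events noted at control-arm scans, and admissions that follow a scan, should not be removed or listed apart, because they are real events under the comparator strategy.

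The cost is one eCRF form, short protocol wording and some extra data entry. No added visit or scan is needed.
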